## **14.2 INQOVI® (DECITABINE AND CEDAZURIDINE)**

INQOVI is a combination of decitabine, a nucleoside metabolic inhibitor, and cedazuridine, a cytidine deaminase inhibitor, indicated for treatment of adult patients with myelodysplastic syndromes (MDS).

### **14.2.1 Source/Acquisition and Accountability**

For participant administration, decitabine and cedazuridine will be purchased by the NIH Clinical Center Pharmacy Department from commercial sources.

### **14.2.2 Toxicity**

Fatal and serious myelosuppression and infectious complications can occur. Can cause fetal harm. Most common adverse reactions (incidence  $\geq 20\%$ ) are fatigue, constipation, hemorrhage, myalgia, mucositis, arthralgia, nausea, dyspnea, diarrhea, rash, dizziness, febrile neutropenia, edema, headache, cough, decreased appetite, upper respiratory tract infection, pneumonia, and transaminase increased. The most common Grade 3 or 4 laboratory abnormalities ( $\geq 50\%$ ) were leukocytes decreased, platelet count decreased, neutrophil count decreased, and hemoglobin decreased. ([57-59](#))

### **14.2.3 Formulation and preparation**

INQOVI (decitabine and cedazuridine) tablets, for oral use contain 35 mg decitabine and 100 mg cedazuridine. The tablets are biconvex, oval-shaped, film-coated, red and debossed with "H35" on one side. Each film-coated tablet contains the following inactive ingredients: lactose monohydrate, hypromellose, croscarmellose sodium, colloidal silicon dioxide, and magnesium stearate. The film coating material contains polyvinyl alcohol, titanium dioxide, polyethylene glycol, talc, and iron oxide red.

#### 14.2.4 Stability and Storage

Each tablet should be stored at 20°C to 25°C. Excursions of the tablet are permitted to 15°C to 30°C. Any unused portion of the tablet should be discarded using special handling and disposal procedures.

#### 14.2.5 Administration Procedures

See Section [3.2.2](#) for details.

#### 14.2.6 Incompatibilities

Avoid coadministration of INQOVI with drugs that are metabolized by cytidine deaminase (CDA) enzymes, such as gemcitabine, cytarabine, and capecitabine.

## 16 LIST OF ABBREVIATIONS

Abbreviation	Term
ACAT	Ability to Consent Assessment Team
AE	Adverse Event/Adverse Experience
AESI	Adverse Event/Experience of Special Interest
ANC	Absolute neutrophil count
BTRIS	Biomedical Translational Research Information System
CCR	Center for Cancer Research
CDA	Confidential Disclosure Agreement
CFR	Code of Federal Regulations
CNS	Central nervous system
CONSORT	Consolidated Standards of Reporting Trials
COV	Close-out Visit
CR	Complete Response
CSR	Clinical Study Report
CRADA	Cooperative Research and Development Agreement
CT	Computed Tomography
CTA	Clinical Trials Agreement
CTCAE	Common Terminology Criteria for Adverse Events
DLT	Dose-limiting toxicity
DTA	Data Transfer Agreement
EC	Ethics Committee
eCRF	Electronic Case Report Form
ECOG	Eastern Cooperative Oncology Group
EFS	Event-free survival
EKG	Electrocardiogram
FDA	Food and Drug Administration
FWA	Federal-Wide Assurance
GCP	Good Clinical Practice
GDS	Genomic Data Sharing
GLP	Good Laboratory Practices
GMP	Good Manufacturing Practices
HBV	Hepatitis B virus
HCV	Hepatitis C virus
HHS	Health and Human Services
HIV	Human immunodeficiency virus
IB	Investigator's Brochure
IBC	Institutional Biosafety Committee
ICD/ICF	Informed Consent Document/Form
ICH	International Council on Harmonisation
IMV	Interim Monitoring Visit
IND	Investigational New Drug
IOCBP	Individuals of childbearing potential

Abbreviation	Term
IRB	Institutional Review Board
IRBO	Institutional Review Board Office
IV	Intravenous
LAR	Legally Authorized Representative
MRI	Magnetic Resonance Imaging
MTA	Material Transfer Agreement
MTD	Maximal tolerated dose
N	Number (typically refers to subjects)
NCT	National Clinical Trial (number)
NDA	New Drug Application
NIH	National Institutes of Health
NOS	Not otherwise specified
OHSRP	Office for Human Subjects Research Protections
OHRP	Office for Human Research Protections
OS	Overall survival
OSRO	Office of Sponsor and Regulatory Oversight
PD	Progressive Disease
PET	Positron Emission Tomography
PFS	Progression-free survival
PI	Principal Investigator
PR	Partial Response
PS	Performance Status
QA	Quality Assurance
QC	Quality Control
rCR	Revised Common Rule
RECIST	Response Evaluation Criteria in Solid Tumors
RP2D	Recommended Phase II dose
SAE	Serious Adverse Event/Serious Adverse Experience
SAV	Site Assessment Visit
SIV	Site Initiation Visit
SD	Stable Disease
SMC	Safety Monitoring Committee
SOP	Standard Operating Procedure
ULN	Upper limit of normal
US	United States
WHO	World Health Organization

## 17 APPENDICES

### 17.1 APPENDIX A: PERFORMANCE STATUS CRITERIA

ECOG Performance Status Scale		Karnofsky Performance Scale	
Grade	Descriptions	Percent	Description
0	Normal activity. Fully active, able to carry on all pre-disease performance without restriction.	100	Normal, no complaints, no evidence of disease.
		90	Able to carry on normal activity; minor signs or symptoms of disease.
1	Symptoms, but ambulatory. Restricted in physically strenuous activity, but ambulatory and able to carry out work of a light or sedentary nature (e.g., light housework, office work).	80	Normal activity with effort; some signs or symptoms of disease.
		70	Cares for self, unable to carry on normal activity or to do active work.
2	In bed <50% of the time. Ambulatory and capable of all self-care, but unable to carry out any work activities. Up and about more than 50% of waking hours.	60	Requires occasional assistance, but is able to care for most of his/her needs.
		50	Requires considerable assistance and frequent medical care.
3	In bed >50% of the time. Capable of only limited self-care, confined to bed or chair more than 50% of waking hours.	40	Disabled, requires special care and assistance.
		30	Severely disabled, hospitalization indicated. Death not imminent.
4	100% bedridden. Completely disabled. Cannot carry on any self-care. Totally confined to bed or chair.	20	Very sick, hospitalization indicated. Death not imminent.
		10	Moribund, fatal processes progressing rapidly.
5	Dead.	0	Dead.

## 17.2 APPENDIX B: 2016 WHO CLASSIFICATION FOR MYELODYSPLASTIC SYNDROME

Reference: Arber, DA, et al.([1](#))

### **Myelodysplastic syndromes (MDS)**

- **MDS with single lineage dysplasia (MDS-SLD)**
- **MDS with ring sideroblasts (MDS-RS)**
  - **MDS-RS and single lineage dysplasia**
  - **MDS-RS and multilineage dysplasia**
- **MDS with multilineage dysplasia (MDS-MLD)**
- **MDS with excess blasts**
- **MDS with isolated del(5q)**
- **MDS, unclassifiable**
- ***Provisional entity: Refractory cytopenia of childhood***

### 17.3 APPENDIX C: REVISED INTERNATIONAL PROGNOSTIC SCORING SYSTEM (IPSS-R) FOR MYELODYSPLASTIC SYNDROMES

Prognostic variable	Score						
	0	0.5	1.0	1.5	2.0	3.0	4.0
Cytogenetics*	Very good		Good		Intermediate	Poor	Very poor
Bone marrow blast (percent)	≤2		>2 to <5		5 to 10	>10	
Hemoglobin (g/dL)	≥10		8 to <10	<8			
Platelets (cells/microL)	≥100	50 to 100	<50				
Absolute neutrophil count (cells/microL)	≥0.8	<0.8					
Risk group		IPSS-R score		Median overall survival (years)		Median time to 25 percent AML evolution (years)	
Very low		≤1.5		8.8		>14.5	
Low		>1.5 to 3.0		5.3		10.8	
Intermediate		>3 to 4.5		3.0		3.2	
High		>4.5 to 6		1.6		1.4	
Very high		>6		0.8		0.7	

AML: acute myeloid leukemia; MDS: myelodysplastic syndromes.

\* Cytogenetic definitions:

Very good: -Y, del(11q)

Good: Normal, del(5q), del(12p), del(20q), double including del(5q)

Intermediate: del(7q), +8, +19, i(17q), any other single, double not including del(5q) or -7/del(7q), or independent clones

Poor: -7, inv(3)/t(3q)/del(3q), double including -7/del(7q), complex: 3 abnormalities.

Very poor: Complex: >3 abnormalities

*This research was originally published in Blood. Greenberg PL, Tuechler H, Schanz J, et al. Revised International Prognostic Scoring System (IPSS-R) for myelodysplastic syndromes. Blood 2012. Copyright © 2012 the American Society of Hematology.*

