## 2 ELIGIBILITY ASSESSMENT AND ENROLLMENT

### 2.1 ELIGIBILITY CRITERIA

#### 2.1.1 Inclusion Criteria

2.1.1.1 Participants must have histologically or cytologically confirmed MDS by the Laboratory of Pathology, NCI- according to 2016 WHO criteria(1)

AND:

- Cohort 1 (Phase 1) & 2 (Phase 2): have HR-MDS (IPSS-R > 3.5) with inadequate response to hypomethylating agent (HMA) therapy [(received  $\geq$  4 cycles of the standard dose (35 mg decitabine and 100 mg cedazuridine) without prior dose-reductions, with failure to achieve at least a PR or experienced disease progression prior to completing 4 cycles)

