## 2.1.2 Exclusion Criteria

2.1.2.1 Participants with platelet transfusion-refractory thrombocytopenia, with inability to keep platelet threshold above 10K/mcL with transfusions or those with ongoing or uncontrolled hemorrhagic complications.

2.1.2.2 Participants with clinically significant neutropenia, defined as ANC <100 cells/mcL with frequent hospitalizations for infection (average > 1 hospitalization per month in the past 6 months).

2.1.2.3 Participants on treatment with a myeloid growth factor (e.g., G-CSF) within 14 days prior to initiation of study treatment.

2.1.2.4 History of allergic reactions attributed to compounds of similar chemical or biologic composition to HMAs or other agents used in study.

2.1.2.5 Uncontrolled intercurrent illness evaluated by history, physical exam, and chemistries or situations that would limit compliance with study requirements, interpretation of results or that could increase risk to the participant

2.1.2.6 Participants with the following cardiac conditions: symptomatic congestive heart failure, unstable angina pectoris, or uncontrolled cardiac arrhythmia as assessed by electrocardiogram (ECG).

- 2.1.2.7 Pregnancy (confirmed with  $\beta$ -HCG serum or urine pregnancy test performed in individuals of childbearing potential at screening)
- 2.1.2.8 Presence of any other malignancy (except basal and squamous cell carcinoma of the skin, or stable chronic cancers on hormone or targeted therapy) for which participant received systemic anticancer treatment (except maintenance therapy) within 24 months prior to treatment.
- 2.1.2.9 Participants with active/uncontrolled Hepatitis B
- 2.1.2.10 Participants with active/uncontrolled Hepatitis C
- 2.1.2.11 Participants with active/uncontrolled HIV infection or AIDS.
- 2.1.2.12 Participants currently taking contraindicated medications for HIV, Hepatitis B, or Hepatitis C disease control ([Appendix L](#))

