#### 10.4.7 Sub-Group Analyses

Results from phase II will be presented according to MDS-subgroup, disease risk category and genomic features.

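### Appendix C labels the IPSS-R platelet and neutrophil rows in cells per microlitre, but the printed cut-offs fit only x 10^9/L, so literal scoring loses up to 1.5 points

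*Combined protocol and SAP*

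**What the plan says.** Appendix C assigns points for cytogenetics, marrow blasts, hemoglobin, platelets and ANC, then maps the total to five risk groups. The platelet row is labelled "Platelets (cells/microL" and printed as >=100 (0 points), 50 to 100 (0.5) and <50 (1.0). The neutrophil row is labelled "Absolute neutrophil count (cells/microL" and printed as >=0.8 (0 points) and <0.8 (0.5).

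The score is used in two places:

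- **Eligibility.** Participants in both phases must "have HR-MDS (IPSS-R > 3.5) with inadequate response to hypomethylating agent (HMA) therapy" (Section 2.1.1.1). The Précis and the cohort table in Section 2.3.2 repeat the 3.5 threshold.
- **Reporting.** Section 10.4.7 states: "Results from phase II will be presented according to MDS-subgroup, disease risk category and genomic features". It does not name the IPSS-R, but this is the disease risk grouping that the protocol sets out.

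Elsewhere, per-microlitre counts are on a much larger scale. Section 2.1.2 excludes participants "with inability to keep platelet threshold above 10K/mcL with transfusions", and excludes clinically significant neutropenia, "defined as ANC <100 cells/mcL with frequent hospitalizations for infection".

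**The concern.** A scoring table for an inclusion threshold should give the right score when followed as printed. Here the unit and the cut-offs cannot both be right. A participant with 20,000 platelets/mcL is far above 100 cells/microL, and one with 300 neutrophils/mcL is far above 0.8 cells/microL. Both would be scored as having no relevant cytopenia.

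The loss can only lower a score, and it is greatest for participants with the deepest cytopenias. Two things are exposed: whether a participant meets IPSS-R > 3.5, and the risk group in which Phase II results are shown. No sample size, error rate, Simon boundary or toxicity rule depends on it.

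**Working it through.** The plan states no figure to reproduce on this point. The check compares units and then scores the table under both readings.

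**1. Which unit fits.** One litre is 10^6 microlitres, so 50 x 10^9/L = 50,000/mcL.

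| Place | Platelets | Neutrophils |
|---|---|---|
| Appendix C as labelled | 100 and 50 cells/microL | 0.8 cells/microL |
| Section 2.1.2 | 10K/mcL | 100 cells/mcL |
| Section 3.3.2.1, start of next cycle | 50,000/mcL | 1000/mcL |
| Section 4.1.2 | 50 x 10^9/L | 500/mcL |
| Section 6.3.1 and Appendix D, complete remission | 100 x 10^9/L | 1.0 x 10^9/L |

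The Section 2.1.2 values are 10,000/100 = 100 times the table's top platelet cut-off and 100/0.8 = 125 times its ANC cut-off. The Appendix C numbers fit the x 10^9/L entries. That reading is inferred from the protocol alone.

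**2. Points at stake.** On the x 10^9/L reading, platelets add up to 1.0 and ANC up to 0.5, so up to 1.5 together. On the literal reading, platelets of 5,000, 30,000 or 75,000/mcL all score 0 (intended 1.0, 1.0, 0.5). ANC of 1, 100 or 500/mcL all score 0 (intended 0.5 each). A recorded ANC of exactly 0 still scores 0.5.

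**3. Worked example.** Good cytogenetics (1), blasts >2 to <5% (1), hemoglobin <8 (1.5), platelets 30,000/mcL, ANC 500/mcL.

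- x 10^9/L: 1 + 1 + 1.5 + 1.0 + 0.5 = 5.0, High, above 3.5.
- As labelled: 1 + 1 + 1.5 + 0 + 0 = 3.5, Intermediate, not above 3.5.

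**4. All score combinations.** There are 5 x 4 x 3 x 3 x 2 = 360 combinations. Let B be the sum of the cytogenetic, blast and hemoglobin points (60 combinations), and A the intended platelet plus ANC points. A takes six values: 0 (once), 0.5 (twice), 1.0 (twice), 1.5 (once). The intended score is B + A; the literal score is B.

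- *Above 3.5 as intended.* B exceeds 3.5 in 38 of the 60, giving 38 x 6 = 228 combinations. The rest have B at or below 3.5 and are lifted over it by A:

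| B | Number with this B | Values of A that lift it above 3.5 | Combinations |
|---|---|---|---|
| 3.5 | 3 | 5 | 15 |
| 3.0 | 7 | 3 | 21 |
| 2.5 | 2 | 1 | 2 |
| Total | | | 38 |

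  So 228 + 38 = 266 combinations qualify, and 38 of the 266 fall to 3.5 or below on the literal reading. Their intended scores run from 4.0 to 5.0.

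- *Risk group.* Counting those of the 266 where B and B + A lie in different groups (boundaries 3, 4.5 and 6), for B = 2.5, 3.0, 3.5, 4.0, 4.5, 5.0, 5.5 and 6.0 in turn: 2 + 21 + 3 + 24 + 20 + 7 + 12 + 25 = 114.

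- *Either change.* The last five terms have B above 3.5 and sum to 24 + 20 + 7 + 12 + 25 = 88. Adding the 38 gives 126 of 266. No combination moves upward.

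**5. Band overlap.** A platelet value of exactly 100 falls in both >=100 and 50 to 100, a difference of 0.5 point.

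**The case against.** The strongest reply is that nobody would apply the table literally. Fewer than 0.8 neutrophils per microlitre means less than one cell, and Appendix D, directly after it, prints the matching x 10^9/L values. A haematologist would probably see a unit slip. This stands, and it limits the practical risk.

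A reader might also infer that Appendix C decides eligibility. The documents do not say so. Section 2.1.1.1 gives the threshold without citing the appendix, Section 1.2.1 introduces the IPSS-R by literature citation, and Section 10.4.7 names neither. Appendix I points to Appendix C only for the cytogenetic category, and it asks for the score at MDS diagnosis, which may predate referral. Still, the protocol contains no other scoring rule, so anyone checking eligibility against it has only this table.

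A reader might further infer that every participant scores 0 on both items, or that 38/266 and 114/266 are the shares of patients lost or misclassified. Neither is supported. An ANC of 0 still scores 0.5, and Section 2.1.2 excludes an ANC below 100 only with frequent hospitalizations. The counts weight all combinations equally, and the documents give no joint distribution of the components in this population.

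The table carries a reproduction note for a published instrument. Whether the platelet band is printed that way in the source cannot be checked here, and the overlap is minor in any case.

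**Conclusion.** The concern holds as a unit error in the protocol's only IPSS-R scoring table. The labels contradict the protocol's other values by a factor of 1000, and literal use lowers scores by up to 1.5 points, enough to take a High-risk profile of 5.0 to 3.5 and out of eligibility. Among unweighted score combinations above 3.5, 38 of 266 cross the threshold and 114 of 266 drop a risk group; no expected number of patients follows from this.

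The conclusion assumes that x 10^9/L is the intended unit, which every other platelet and neutrophil value compared above supports. It does not show that any participant will be mis-scored. The correction is worth making because the table supports an inclusion threshold, but it leaves the design and its operating characteristics unchanged.

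**What to change.** In Appendix C, relabel the two rows as Platelets (x 10^9/L) and Absolute neutrophil count (x 10^9/L), in line with Appendix D. As a minor tidy-up, change the middle platelet band to 50 to <100 so that 100 falls in one column only.

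The cost is two unit labels and one band edit in a single table, which can go into the next amendment. The cut-off numbers, the eligibility threshold and the analyses stay as they are.

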#### **17.4 APPENDIX D: THE 2006 INTERNATIONAL WORKING GROUP RESPONSE CRITERIA WITH MODIFIED DEFINITIONS FOR HEMATOLOGIC IMPROVEMENT BY THE 2018 INTERNATIONAL WORKING GROUP RESPONSE CRITERIA**

Reference: Platzbecker, U, et al.([54](#))

Category	Response criteria (responses must last at least 4 weeks)
Complete remission	

• Bone marrow: <math>\leq 5\%</math> myeloblasts with normal maturation of all cell lines*

• Persistent dysplasia will be noted*

• Peripheral blood†

• Hgb <math>\geq 11</math> g/dL

• Platelets <math>\geq 100 \times 10^9/L</math>

• Neutrophils <math>\geq 1.0 \times 10^9/L</math>

• Blasts 0%

Partial remission	All CR criteria if abnormal before treatment except: 

• Bone marrow blasts decreased by <math>\geq 50\%</math> over pretreatment but still <math>>5\%</math>

• Cellularity and morphology not relevant

Marrow CR	

• Bone marrow: <math>\leq 5\%</math> myeloblasts and decrease by <math>\geq 50\%</math> over pretreatment

• Peripheral blood: if HI responses, they will be noted in addition to marrow CR

Stable disease	Failure to achieve at least PR, but no evidence of progression for $>8$ weeks
Failure	Death during treatment or disease progression characterized by worsening of cytopenias, increase in percentage of bone marrow blasts, or progression to more advanced MDS FAB subtype than pre-treatment
Relapse after CR or PR	At least 1 of the following: 

• Return to pre-treatment bone marrow blast percentage

• Decrement of <math>\geq 50\%</math> from maximum remission/response levels in granulocytes or platelets

• Reduction in Hgb concentration by <math>\geq 1.5</math> g/dL or transfusion dependence

Cytogenetic response	Complete 

• Disappearance of the chromosomal abnormality without appearance of new ones

 Partial 

• At least 50% reduction of the chromosomal abnormality

Disease progression	For patients with: 

• Less than 5% blasts: <math>\geq 50\%</math> increase in blasts to <math>>5\%</math> blasts

• 5%-10% blasts: <math>\geq 50\%</math> increase to 10% blasts

	
 
• 10%-20% blasts: <math>\geq 50\%</math> increase to <math>>20\%</math> blasts
 
• 20%-30% blasts: <math>\geq 50\%</math> increase to <math>>30\%</math> blasts
 
 
Any of the following:
 
 
• At least 50% decrement from maximum remission/response in granulocytes or platelets
 
• Reduction in Hgb by <math>\geq 2</math> g/dL
 
• Transfusion dependence
 

Survival	
Endpoints:
 
 
• Overall: death from any cause
 
• Event free: failure or death from any cause
 
• PFS: disease progression or death from MDS
 
• DFS: time to relapse
 
• Cause-specific death: death related to MDS
 

MDS, myelodysplastic syndromes; Hgb, hemoglobin; CR, complete remission; HI, hematologic improvement; PR, partial remission; FAB, French-American-British; AML, acute myeloid leukemia; PFS, progression-free survival; DFS, disease-free survival.

To convert hemoglobin from grams per deciliter to grams per liter, multiply grams per deciliter by 10.

\*Dysplastic changes should consider the normal range of dysplastic changes.

†In some circumstances, protocol therapy may require the initiation of further treatment (eg, consolidation, maintenance) before the 4-week period. Such patients can be included in the response category into which they fit at the time the therapy is started. Transient cytopenias during repeated chemotherapy courses should not be considered as interrupting durability of response, as long as they recover to the improved counts of the previous course.

## Hematologic Improvement

Category	Patient pre-trial baseline	Response criteria	
Erythroid response (HI-E)	No Transfusion Dependence at baseline (0 RBC transfusions in 16 weeks)	At least 2 consecutive Hgb measurements $\geq 1.5$ g/dL for a period of minimum 8 weeks in an observation period of 16 to 24 weeks compared with the lowest mean of 2 Hgb measurements (apart from any transfusion) within 16 weeks before treatment onset; only a response duration of at least 16 weeks, however, is considered clinically meaningful	
	Low Transfusion Dependence at baseline (3-7 RBC transfusions in 16 weeks in at least 2 transfusion episodes, maximum 3 in 8 weeks)	Transfusion independence, defined by the absence of any transfusions for at least 8 weeks in an observation period of 16-24 weeks with the same transfusion policy compared with 16 weeks prior to treatment; only a response duration of at least 16 weeks, however, is considered clinically meaningful	
	High Transfusion Dependence at baseline ( $\geq 8$ RBC transfusions in 16 weeks)	Major response	Transfusion independence, defined by the absence of any transfusions over a period of minimum 8 weeks in an

	weeks, $\geq 4$ transfusion episodes in 8 weeks)		observation period of 16-24 weeks with the same transfusion policy compared with 16 weeks prior to treatment; only a response duration of at least 16 weeks, however, is considered clinically meaningful
		Minor response	A reduction by at least 50% of RBCs over a minimum of 16 weeks with the same transfusion policy, compared with 16 weeks prior to treatment
Platelet response (HI-P)	Pre-treatment PLT $<100 \times 10^9/L$	
 
Absolute increase of <math>30 \times 10^9/L</math> for patients starting with <math>>20 \times 10^9/L</math> PLTs or
 
Increase from <math><20 \times 10^9/L</math> to <math>>20 \times 10^9/L</math> and by at least 100%
 
 
In addition:
 
 
In addition, evolution of bleeding symptoms is to be taken into account
 
Increments of platelets also for patients with a pre-treatment PLT count of <math>\geq 100 \times 10^9</math> are to be reported
 
	
Neutrophil response (HI-N)	Pre-treatment ANC $<1.0 \times 10^9/L$	
 
At least 100% increase and an absolute increase <math>>0.5 \times 10^9/L</math>
 
Increments of neutrophils also for patients with a pre-treatment ANC of <math>\geq 1.0 \times 10^9/L</math> are to be reported
 
	

